4.1.1 Standard Descriptive Statistics

Continuous Variables

Unless specified otherwise, the following standard descriptive statistics will be provided for continuous variables by treatment sequence: number of subjects with a non-missing value of the variable (n), number of subjects with a missing value of the variable, mean, standard deviation (SD), median, 25th and 75th percentiles, minimum, and maximum.

Categorical Variables

Unless specified otherwise, the following standard descriptive statistics will be presented for categorical values by treatment sequence: number of subjects with non-missing data, number of subjects with missing data as well as the number and percentage within each category of the parameter. The ‘missing’ category will not be included in the percentage computation, unless otherwise specified. Details will be defined in the table shells. If no subjects fall in any categories, “0” will be reported.

By convention, for a variable the sum of the number of subjects with non-missing and missing data will always be equal to the number of subjects specified in the header of the corresponding summary table, unless otherwise specified.

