4.1.2 Definition of Baseline, Visits and Visit Windows

In general, the baseline is defined as the last available (non-missing) value (scheduled or unscheduled) prior to the first dose in the open-label extension period. For the efficacy endpoints, the 5-D itch scale and the Skindex-10 scale score, analyses will be conducted based on two different baseline definitions. The first definition is that baseline is the last available (non-missing) value (scheduled or unscheduled) prior to the first dose in the open-label extension period. The second definition is that baseline is the last available value (scheduled or unscheduled) before or on the same day as randomisation or if missing as any values during Week 1 (\leq Day 7). As a general rule for safety and efficacy related summaries (e.g., tables), the visit label mentioned in [Table 3](#) will be used to present the corresponding data by study visits for the open-label extension period.

Table 3: Study Visits and Planned Assessment Window for Safety and Efficacy Analysis

Visit	Visit Label	Planned Target Day (Assessment Time Window) for by visit parameters
EoT (Double-blind) / Day 1 (Open-label)	Baseline (Open-label)	Day 1 (\leq Day 1) ^a
Week 2 (Open-label)	Open-label Week 2	Day 8 to Day 14 (Day 8 to Day 21)
Week 4 (Open-label)	Open-label Week 4	Day 22 to Day 28 (Day 22 to Day 35)
Week 6 (Open-label)	Open-label Week 6	Day 36 to Day 42 (Day 36 to Day 49)
Week 8 (Open-label)	Open-label Week 8	Day 50 to Day 56 (Day 50 to Day 63)
Week 10 (Open-label)	Open-label Week 10	Day 64 to Day 70 (Day 64 to Day 77)
Week 12 (Open-label)	Open-label Week 12	Day 78 to Day 84 (Day 78 to Day 91)
EoT/ET (Open-label)	Open-label Week 14	Day 99 (Day 92 to maximum day of [Day EoT/ET visit and Day 99])
	Last Post-baseline (Open-label) ^b	
Follow-up (Open-label)	Follow-up (Open-label) ^c	EoT/ET visit + 7 Days ([EoT/ET visit + 1] to maximum day of [EoT/ET visit + 10, 109])

^a Study Day 1 is defined as the first dose date during the open-label extension period (as per the “Study Drug Administration- Open Label” eCRF page).

^b The last post-baseline visit is defined as the latest value recorded for a given parameter, not including the Follow-up Visit or any visits following the End of Treatment/Early Termination Visit. To be displayed for safety endpoints summary tables.

^c Follow-up (Open-label) is applicable for safety analysis only.

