4.7 Efficacy Analyses

Itch-related QoL including 5-D itch scale and Skindex-10 scale will be collected for the evaluation of the efficacy in the open-label extension period.

4.7.1 5-D Itch Scale

The 5-D Itch Scale was developed as a brief, multidimensional questionnaire designed to be useful as an outcome measure in clinical trials. The 5 dimensions of itch being assessed are degree, duration, direction, disability, and distribution (see protocol Appendix 4).

The duration, degree, and direction domains each include 1 item, while the disability domain has 4 items. All items of the first 4 domains were measured on a 5-point Likert scale. The distribution domain included 16 potential locations of itch, including 15 body part items and 1 point of contact with clothing or bandages.

Single-item domain scores (duration, degree, and direction) are equal to the value indicated below the response choice (range 1-5). The disability domain includes 4 items that assess the impact of itching on daily activities: sleep, leisure/social activities, housework/errands, and work/school. The score for the disability domain is calculated by taking the highest score on any of the 4 items. For the distribution domain, the number of affected body parts is tallied (potential sum 0-16), and the sum is sorted into 5 scoring bins: sum of 0-2 = score of 1, sum of 3-5 = score of 2, sum of 6-10 = score of 3, sum of 11-13 = score of 4, and sum of 14-16 = score of 5.

The scores of each of the 5 domains are calculated separately and then summed together to obtain a total 5-D score. 5-D scores can potentially range between 5 (no pruritus) and 25 (most severe pruritus).

Total 5-D Itch score = duration score (single item) + degree score (single item) + duration score (single item) + maximum (4 disability items) + category score based on sum of affected body parts.

The scoring manual does not give specific direction regarding scoring when some questions are missing; therefore, each domain and the total score will be set to missing when any of their individual components are missing, with the exception of the disability domain. The maximum of any items present for disability will be used for that domain.

Analyses

The 5-D itch scale scores will be analysed using an MMRM model. The model will contain treatment sequence, week, and treatment-by-week interaction as fixed effects, and baseline score and the randomization stratification variables as covariates.

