Two independent analyses will be presented, one using baseline from the open-label extension period and one using baseline from the double-blind period. The first analysis will include all visits in the open-label extension period, with the first baseline definition defined in section [4.1.2](#). The second analysis will include all visits from both the double-blind and open-label periods, with the second baseline definition defined in section [4.1.2](#).

Separate models will be used for the 2 different changes from baselines described above. An unstructured covariance matrix will be used to model the within-subject errors. Should the model fail to converge, a compound symmetric covariance matrix will be used instead. The Kenward-Roger2 approximation will be used to estimate the denominator degrees of freedom. Missing scores will not be imputed. Assuming that the data are missing at random (MAR), the estimates calculated from the MMRM described above are unbiased.

Standard descriptive statistics will be reported for each time point on the values and changes from baseline along with the least squares (LS) means, standard errors, 95% confidence intervals (CIs), and differences from baseline within each treatment sequence reported with LS means, standard errors, and 95% CIs. Plots will also be created.

The above analyses for the 5-D itch scale total score will be repeated for each of its domain scores.

As a separate analysis, the number and percentage of subjects that have a 5 point or greater improvement of the 5-D itch scale total score will be reported by visit and treatment sequence. Additionally, the percentage and 95% CIs estimated using a logistic regression model, containing terms for treatment sequence, baseline total 5-D score, use of anti-itch medication during the week prior to randomization, and presence of specific medical conditions, will be presented. This analysis will be performed using the baseline from the double-blind period.

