4.7.2 Skindex-10 scale

Skindex-10 Scale

Developed specifically for uremic pruritus, the Skindex-10 Scale (see protocol Appendix 3) is an instrument for measurement of quality of life. Subjects are asked the question “During the past week, how often have you been bothered by” and respond by filling in 1 of 7 circles numbered from 0 (labelled with the anchor phrase “never bothered”) to 6 (labelled as “always bothered”) for each of the 10 questions.

The total score is the sum of the numeric value of each answered question.

Additionally, the total score is subdivided into 3 domain scores, which are sums of the scores of the following questions: disease domain (questions 1 to 3), mood/emotional distress domain (questions 4 to 6), and social functioning domain (questions 7 to 10).

The scoring manual does not give specific direction regarding scoring when some questions are missing; therefore, the three domains and the total score will be set to missing when any of their individual components are missing.

Analyses

The analyses for the Skindex-10 scales total score as well as the domain scores will be the same as the 5-D itch scale. The same MMRM model will be used in two independent analyses using different time points for the baseline values and changes from baseline using each of the baselines, as described for 5-D itch in Section [4.7.1](#). As a separate analysis, the number and percentage of subjects that have a 15 point or greater improvement of the Skindex-10 scales total score will be reported by visit and treatment sequence. Additionally, the percentage and 95% CIs estimated using a logistic regression model, containing terms for treatment sequence, baseline Skindex-10 scales total score, use of anti-itch medication during the week prior to randomization, and presence of specific medical conditions, will be presented. This analysis will be performed using the baseline from the double-blind period.

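### Must the SAP state the baseline value and stratum weights behind the open-label LS means?

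*SAP*

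**What the plan says.** SAP 4.7.1 gives the model: "The model will contain treatment sequence, week, and treatment-by-week interaction as fixed effects, and baseline score and the randomization stratification variables as covariates". Two versions are fitted. For one, "The first analysis will include all visits in the open-label extension period, with the first baseline definition"; SAP 4.1.2 defines that baseline: "baseline is the last available (non-missing) value (scheduled or unscheduled) prior to the first dose in the open-label extension period". For the other, "The second analysis will include all visits from both the double-blind and open-label periods, with the second baseline definition", which is tied to randomisation. SAP 4.7.2 carries this over to Skindex-10: "The same MMRM model will be used in two independent analyses using different time points for the baseline values".

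The promised output is "differences from baseline within each treatment sequence reported with LS means, standard errors, and 95% CIs". Observed results go with it: "Standard descriptive statistics will be reported for each time point on the values and changes from baseline along with the least squares (LS) means". SAP 4.1.1 confirms the layout: "the following standard descriptive statistics will be provided for continuous variables by treatment sequence". SAP 4.1 names SAS 9.4 or later as the software. No LS-mean option is given.

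Protocol 12.8.2 uses a pre-randomisation Day 1 baseline for both scales, fits each period on its own, and plans an adjusted difficelikefalin-minus-placebo difference at Week 12 of the double-blind period. It names no LS-mean reference values there, and neither does Protocol 12.8.1 for the primary MMRM. Protocol 12.11 leaves baseline definitions to the SAP. SAP 1.2 lists only the two added responder analyses as changes from the protocol.

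**The concern.** An LS mean is a model prediction at chosen covariate values. In a treatment contrast from an additive model those values cancel. Here the SAP reports each sequence's own LS mean, so they do not.

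The open-label baseline makes this visible. It is measured after 12 weeks of placebo or difelikefalin, so randomisation does not balance it, and a drug that works would leave the two sequences at different levels. Evaluated at one common baseline, each LS-mean change is pulled away from what that sequence actually experienced, one up and the other down. The stratification variables add a second choice: as class factors with equal weights they give different LS means than as numeric covariates or with observed weights.

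Two programmers could therefore print different within-sequence values from the same data, and a reader could take an adjusted value for the sequence's own change. The protocol does not settle the choice.

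**Working it through.** The documents give no planned figure for this analysis. The 116 per group and 258 in total belong to the Week 4 WI-NRS endpoint and do not enter here. The slope, baseline gap, stratum effects and prevalences below are all assumptions.

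**Baseline part.** For sequence s, with baseline as an additive covariate:

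LS mean change = observed mean change + b × (reference baseline − mean baseline of s)

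Take the overall mean as reference, equal sequence sizes, and let Placebo/Difelikefalin sit d points higher. Its mean baseline is then d/2 above the overall mean and the other's d/2 below. The shifts are −b·d/2 and +b·d/2, so |b|·d/2 in opposite directions.

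| b | d | shift per sequence (5-D points) |
|---|---|---|
| any | 0 | 0 |
| -0.3 | 1 | 0.3 × 1/2 = 0.15 |
| -0.5 | 2 | 0.5 × 2/2 = 0.50 |
| -0.6 | 2 | 0.6 × 2/2 = 0.60 |
| -0.7 | 3 | 0.7 × 3/2 = 1.05 |

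**Stratum part.** Moving from observed to equal weights shifts both sequences by effect × (0.5 − prevalence), summed over the two factors. With prevalences of 30% and 15% and an effect of 0.5 each: 0.5 × 0.20 + 0.5 × 0.35 = 0.275. The shift is zero if the factors enter as numeric covariates evaluated at their means.

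**Both together.** One simulated visit with 20,000 subjects, baselines 14 and 12, b = -0.5, prevalences 30% and 10%, effects of 1 each:

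| LS means evaluated at | Placebo/Difelikefalin | Difelikefalin/Difelikefalin | difference |
|---|---|---|---|
| common baseline, equal weights | -0.51 | 0.00 | 0.51 |
| common baseline, observed weights | -1.07 | -0.56 | 0.51 |
| own baseline, observed weights | -1.57 | -0.05 | 1.52 |
| observed mean change | -1.57 | -0.06 | |

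The within-sequence values move. At a common baseline the difference between sequences does not depend on the weights. The last row is what the SAP prints anyway.

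**Is the default interval wrong?** A single-visit ANCOVA was simulated with 100 per sequence, SD 4.5, b = -0.4 and 8,000 runs. For gaps of 0, 0.5, 1, 1.5 and 2 points, the 95% interval of the common-baseline LS mean covers the sequence's own mean change 94, 93, 90, 86 and 79% of the time. It covers its own target, the mean change at the common baseline, 95% of the time throughout. The observed mean change also covers its own target 95% of the time. The lower figures arise only when the LS mean is judged against a quantity the SAP never assigns to it.

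**The case for a change.** The best case for a change is that a software default is not a pre-specification. It depends on how the strata are coded, and SAP 4.7.1 simply calls them covariates. The reported quantity is within-sequence, the baseline is post-randomisation, and a sentence would cost almost nothing. SAP 1.2 is also incomplete: the second model pools the two periods where Protocol 12.8.2 keeps them apart, and this is not listed.

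The factual parts stand: the reference values are unstated, and the pooling is missing from SAP 1.2. The consequence does not follow.

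- An analyst using the named software would by default get LS means at the overall mean baseline, with equal weights over class levels. Protocol 12.8.1, in its imputation text, calls the strata categorical, which points to class factors. Own-sequence baselines would need a special request that nothing in the text suggests.
- The gap is not caused by a departure from the protocol's model. The protocol gives no reference values for any MMRM, so an identical model would leave the same silence. The terms and stratification factors match, and so does the sequence grouping in Protocol 12.4.4.
- The open-label baseline is a definition that Protocol 12.11 hands to the SAP. The protocol's adjusted difference is written for drug against placebo at double-blind Week 12, and the extension has no placebo arm. That it had to be carried into the extension is an inference.
- The unlisted pooling is a clerical omission. SAP 4.7.1 states the pooling openly, and SAP section 1 gives the SAP precedence.

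**Conclusion.** No change to the plan. This is missing detail of the kind analysts fill sensibly. Reporting at a common baseline and reporting at each sequence's own baseline are both legitimate, and the default choice gives an interval that is correct for what it estimates. A reader who wants each sequence's own change has the observed values beside it at every time point. The table and figure titles in SAP Appendix 1 already identify the model-based results as MMRM or LS-mean output.

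The size cannot be fixed, because the documents give neither the slope nor the baseline gap. Under the assumptions above, the baseline part is 0 to 0.6 points per sequence for slopes of -0.3 to -0.6 and gaps up to 2, reaching 1.05 points at a slope of -0.7 and a gap of 3. The stratum part is 0.275 points in the worked example and can be zero. The SAP plans no p-value, between-sequence contrast or decision on these values, and the primary endpoint, alpha and sample size are untouched.

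The table shells and the separate double-blind SAP were not available. They may already record the LS-mean options.

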4.7.2 Skindex-10 scale

Skindex-10 Scale

Developed specifically for uremic pruritus, the Skindex-10 Scale (see protocol Appendix 3) is an instrument for measurement of quality of life. Subjects are asked the question “During the past week, how often have you been bothered by” and respond by filling in 1 of 7 circles numbered from 0 (labelled with the anchor phrase “never bothered”) to 6 (labelled as “always bothered”) for each of the 10 questions.

The total score is the sum of the numeric value of each answered question.

Additionally, the total score is subdivided into 3 domain scores, which are sums of the scores of the following questions: disease domain (questions 1 to 3), mood/emotional distress domain (questions 4 to 6), and social functioning domain (questions 7 to 10).

The scoring manual does not give specific direction regarding scoring when some questions are missing; therefore, the three domains and the total score will be set to missing when any of their individual components are missing.

Analyses

The analyses for the Skindex-10 scales total score as well as the domain scores will be the same as the 5-D itch scale. The same MMRM model will be used in two independent analyses using different time points for the baseline values and changes from baseline using each of the baselines, as described for 5-D itch in Section [4.7.1](#). As a separate analysis, the number and percentage of subjects that have a 15 point or greater improvement of the Skindex-10 scales total score will be reported by visit and treatment sequence. Additionally, the percentage and 95% CIs estimated using a logistic regression model, containing terms for treatment sequence, baseline Skindex-10 scales total score, use of anti-itch medication during the week prior to randomization, and presence of specific medical conditions, will be presented. This analysis will be performed using the baseline from the double-blind period.

4.8 Safety Analyses

All safety analyses are to be performed by treatment sequence and all sequences pooled using the OL-SAF and are to be descriptive. Missing values will not be imputed unless stated otherwise, please refer to [Section 4.1.9](#).

4.8.1 Adverse Events

AEs data are collected from the time the informed consent form (ICF) is signed by the subject. The AE reporting period ends at the last study contact. Missing dates/partial dates of AEs will be handled as per [Section 4.1.9](#).

AEs relative to the open-label extension period are identified as any AE with an onset date on or after the first dose of difelikefalin in the open-label extension period.

All tabular adverse event summaries will only include AEs relative to the open-label extension period.

An AE will be classified as related to study drug if the relationship to study drug was recorded as 'Certain' or 'Probable/Likely' or 'Possible' in eCRF, as determined by the investigator. An AE will be classified as unrelated to study drug if the relationship to study drug was recorded as 'Unlikely' or 'Unrelated' in eCRF as determined by the investigator.

An SAE is defined as an AE when "Is this AE considered as Serious?" on the "Adverse Event" eCRF page is "Yes".

An AE leading to investigational product interruption is defined as an AE where the action taken with study drug is "Drug Interrupted" on the "Adverse Event" eCRF page. An AE leading to investigational product discontinuation is defined as is defined as an AE where the action taken with study drug is "Drug Withdrawn" on the "Adverse Event" eCRF page. An AE leading to early study termination is defined as an AE where other action taken is "Early Study Termination".

Adverse Events of Special Interest (AESI)

An AESI is a medical occurrence specific to the product or program. Any AE with the following MedDRA PT is to be identified as an AESI:

- gait disturbance
- fall
- dizziness
- somnolence
- seizure
- syncope
- mental status changes
- mood altered
- feeling abnormal
- sinus tachycardia, tachycardia, and tachyarrhythmia
- palpitations

The number and percentage of subjects experiencing AEs will be summarised by treatment sequence and all sequences pooled. AEs will be summarised by severity. In the instance where a subject reports the same AE multiple times then the event with the worst severity will be tabulated. AEs will also be summarised by relationship to investigational product. In the instance where a subject reports the same AE multiple times then the event with the strongest relationship to investigational product will be tabulated. AEs will be reported on a per-subject and per-event basis. On a per-subject basis this means a subject contributes only once to the count for a given AE (MedDRA SOC or PT using the worst severity and the strongest relationship). The number of events will be reported as well in the summary tables. Multiple occurrences of the same AE in one subject during the same treatment in the trial will be counted as multiple events in the frequency counts for AEs.

An overall summary table is to be provided, presenting for each treatment sequence and all sequences pooled, the number and percentage of subjects as well as the number of events for:

- AEs
- Treatment-related AEs
- SAEs
- Treatment-related SAEs
- AEs leading to study drug interruption
- AEs leading to study drug discontinuation
- AEs leading to early study termination
- Treatment-related AEs leading to study drug discontinuation
- AESIs
- Related AESIs
- AEs leading to death

In addition, the following summary tables will be presented and will include the number and percentage of subjects as well as the number of events for:

- AEs by SOC and PT
- SAEs by SOC and PT
- Related AEs by SOC and PT
- Related SAEs by SOC and PT
- AEs leading to study drug discontinuation by SOC and PT
- Related AEs leading to study drug discontinuation by SOC and PT
- AEs by SOC, PT, and maximum severity
- AEs by SOC, PT, and strongest relationship
- AESIs by PT
- Related AESIs by PT
- Most common AEs ($\geq 2\%$ or more of subjects in any treatment group) by PT

Incidence for SOC will be presented by decreasing frequency overall and then alphabetically; for preferred terms, incidence will be presented by decreasing frequency overall within each SOC (if applicable) and then alphabetically.

All AEs will be listed by subject in chronological order. Separate listings will be generated for:

- AEs
- SAEs
- AEs leading to study drug discontinuation

- AEs leading to early study termination
- AESIs
- Deaths
- AEs starting in the double-blind period and leading to study drug discontinuation, early study termination or death in the open-label extension period

